7.1.2 Adverse Events of Special Interest

Table 2. AEs of Special Interest for This Registry

Serious and non-serious opportunistic infections, including the following bacterial, fungal, viral and parasitic infections: Aspergillus, Blastomyces, Candida, Coccidioides, Cryptococcal, Cytomegalovirus, Histoplasma, Listeria, Nocardia, Paracoccidioides, Pneumocystis, Toxoplasma, Tuberculosis, Herpes, Bacillary angiomatosis, Mucormycosis, Progressive Vaccinia, Zygomycosis, BK virus, and JC virus

L	y	m	ıp	h	O.	m	ıa

Hepatosplenic T-cell lymphoma

Leukemia

Non-melanoma skin cancer (NMSC)

Other malignancies (except lymphoma, leukemia and NMSC)

Immune reactions including lupus, lupus-like reactions, and severe allergic reactions

Congestive heart failure (CHF)

Cerebrovascular accident (CVA)

Myocardial infarction (MI)

CNS demyelinating disorders (including MS and Guillain-Barré syndrome)

Hepatic events that are serious or lead to permanent discontinuation of HUMIRA (e.g., persistent liver function test abnormalities, acute liver failure and other serious hepatic events)

Hematologic events that are serious or lead to permanent discontinuation of HUMIRA (e.g., aplastic anemia, Granulocytopenia, Granulocyte Maturation Arrest, Leukopenia, Neutropenia, Pancytopenia and Thrombocytopenia)

Worsening of Psoriasis

Vasculitis

Diverticulitis

Intestinal perforation

In addition, to the SAEs and AEs of Special Interest (Table 2), AEs that lead to permanent discontinuation of HUMIRA® will be collected.

Psoriasis HUMIRA® Registry

For patients participating in the direct to HCP process in addition to surgeries, hospitalizations, deaths, and the events listed as AEs of Special Interest (Table 2), AEs of Special Interest that lead to permanent discontinuation of HUMIRA® will be collected.

During the course of the registry, additional AEs of Special Interest may be identified by AbbVie. Updates to the AEs of Special Interest will be maintained and collected through the eCRF system. Sites will be trained on all updates to the eCRF system.

The physician will assess and record any additional information on the AEs of Special Interest in detail on the AE of Special Interest eCRF.

The physician will assess all reported AEs for seriousness and follow the requirements/timelines for reporting any AE that fulfills the criteria of an SAE, as defined in Section 7.1.3.

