10.0 Data Analysis Plan

10.1 Analyzable Populations

All Treated Patient Population is defined as patients who receive at least one dose of HUMIRA® in the registry.

New Prescription Patient Population is defined as patients who have newly initiated HUMIRA[®] therapy within 4 weeks prior to the entry into the registry and who receive at least one dose of HUMIRA[®] in the registry (the New Prescription Population is a subset of the All Treated Patient Population).

The All Treated Patient Population and the New Prescription Patient Population will be used for safety and effectiveness analysis.

In addition, the Intermittent Treatment Population, defined as patients who have at least 2 treatment interruption periods with at least 3 treatment periods (Figure 1), will be used for the safety analysis. A treatment interruption period is defined as greater than 70 consecutive days during which the patient does not receive any HUMIRA® treatment. The treatment interruption period starts from 71 days after the last dose of HUMIRA® in

the preceding treatment period and up to the day prior to the first dose of $HUMIRA^{@}$ in the subsequent period. A treatment period is defined as at least one dose of $HUMIRA^{@}$ up to 70 days after the last dose of $HUMIRA^{@}$.

Last Dose First Dose First Dose Day 70 Post-TI (#1) Pre-TI (#1) On Drug Off Drug = TI Drug On 70 days after last dose Treatment Period 1 -Treatment Interruption 1 -**Treatment Period** through 70 days after last dose Begins Day 71 after last dose 2, 3....N

[figure not shown]
Figure 1. Treatment Period and Treatment Interruption (TI) Period

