10.3 Safety Analyses

[figure not shown]
Five main safety analyses will be reported from this registry: four analyses will summarize data through the end-of-registry (as defined in Section 12.0) and one will exclude the HCP Process. The details of the analyses are in Section 10.3.1, Section 10.3.2, and Section 10.3.3. If a patient is not covered by any of the analysis populations, but experiences an AE, this AE will be reported in a separate listing.

Observational AEs: SAEs, AEs of Special Interest and AEs that lead to permanent discontinuation of HUMIRA[®] occurring from the first day in the registry (enrollment visit or date of informed consent, through the last contact (as defined in Section 10.3.1) irrespective of drug treatment duration.

Registry Treatment-emergent AEs: SAEs, AEs of Special Interest and AEs that lead to permanent discontinuation of HUMIRA® occurring from the first recorded dose of HUMIRA® in the registry through 70 days after the last dose excluding AEs occurring during treatment interruptions (as defined in Section 10.1).

All Treatment Emergent AEs: SAEs, AEs of Special Interest and AEs that lead to permanent discontinuation of HUMIRA® occurring from the first recorded dose of HUMIRA® (initial dose) through 70 days after the last dose excluding AEs occurring during treatment interruptions (as defined in Section 10.1.

AEs for intermittent treatment: SAEs, AEs of Special Interest and AEs that lead to permanent discontinuation of HUMIRA® in the Intermittent Treatment Population.

Observational AEs excluding HCP process: SAEs, AEs of Special Interest and AEs that lead to permanent discontinuation of HUMIRA® occurring from the first day in the registry through the last contact excluding the HCP process.

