10.3.2 Analysis of Treatment-Emergent AEs

Registry Treatment-emergent SAEs, AEs of Special Interest and AEs that lead to permanent discontinuation of HUMIRA® and All Treatment-emergent SAEs, AEs of Special Interest and AEs that lead to permanent discontinuation of HUMIRA® will be summarized.

Registry Treatment-emergent AEs includes AEs occurring from the first day in the registry to 70 days after the last dose of HUMIRA® excluding:

- 1. AEs occurring during TI which are more than 70 days after the last dose of HUMIRA[®] prior to the TI.
- 2. AEs occurring on or after the first day of the registry, but before the date of the first dose of HUMIRA[®].

All Treatment-emergent AEs include AEs occurring from the first recorded dose of HUMIRA® (i.e., the initial dose) up to 70 days after the last dose of HUMIRA® (excluding AEs during TI which are more than 70 days after the last dose of HUMIRA® prior to TI). For patients enrolled from a prior HUMIRA® study or who initiated commercial HUMIRA® therapy before entering the registry, the summaries will include the events reported during their participation in the previous study, any events reported by retrospective data collection, and any events reported during this registry.

The number and percentage of patients experiencing treatment-emergent SAEs, AEs of Special Interest and AEs that lead to permanent discontinuation of HUMIRA® will be tabulated by body system and MedDRA® preferred term. Rates (event per 100 patient-years of exposure to HUMIRA®, defined in Section 10.2) of SAEs, AEs of Special Interest and AEs that lead to permanent discontinuation of HUMIRA® and the 95% confidence interval will be provided.

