10.3.3 Analysis of AEs for Intermittent Treatment

The following analyses will be performed for the Intermittent Treatment:

- 1. Rates (event per 100 patient-years of exposure to HUMIRA®) of treatment-emergent SAEs, AEs of Special Interest and AEs that lead to permanent discontinuation of HUMIRA® and the 95% confidence interval will be provided.
- 2. Rates (event per 100 patient-years) of SAEs, AEs of Special Interest and AEs that lead to permanent discontinuation of HUMIRA® and the 95% confidence interval over the course of intermittent treatment strategy, defined as from the first day of HUMIRA® injection to the end of the last treatment period, will be provided.

To further evaluate the effect of intermittent treatment on the AE profile, rates of AEs per 100 patients-years of exposure to HUMIRA® will be analyzed for each treatment period for the subgroups of patients with at least 3, 4, and 5 or more TIs.

	Overall	1 st Treatment Period	2 nd Treatment Period	3 rd Treatment Period	4 th Treatment Period	5 th Treatment Period	6 th + Treatment Period
> 2 TIs ^a	X.XX	X.XX	X.XX	x.xx			
> 3 TIs	X.XX	X.XX	X.XX	x.xx	X.XX		
> 4 TIs	X.XX	X.XX	X.XX	x.xx	x.xx	X.XX	
> 5 TIs	X.XX	X.XX	X.XX	x.xx	x.xx	X.XX	X.XX

a. This is the Intermittent Treatment Population.

Summaries of AEs among patients not in the Intermittent Treatment Population will be provided as a reference.

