mean and standard deviation of change from baseline will be provided for continuous variables. Counts and percentages will be provided for categorical variables.

The effectiveness data will be summarized for the All Treated Patient Population (from the first dose in the registry) and the New Prescription Patient Population. For patients with TI, effectiveness summaries will combine data from all Treatment Periods, excluding the measurements from 14 days after the last dose during a treatment period up to the first dose in the subsequent Treatment Period.

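### Psoriasis flares after stopping are pooled with on-drug events for 70 days, so the Section 10.3.3 AESI rates can rise with the number of stops even if on-drug risk is unchanged

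*Protocol*

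**What the plan says.** - **The event.** Table 2 (Section 7.1.2) lists "Worsening of Psoriasis" as an AESI, without definition or qualifier. Section 7.1.1 treats deterioration of an existing illness as an adverse event and names withdrawal of the drug among the possible sources, so a flare after stopping qualifies.
- **The safety window.** Section 10.3.2 summarises "Registry Treatment-emergent SAEs, AEs of Special Interest and AEs that lead to permanent discontinuation of HUMIRA", with no exception for any AESI. Section 10.3 counts registry events from the first dose "in the registry through 70 days after the last dose excluding AEs occurring during treatment interruptions". The rule for interruptions in Section 10.3.2 is "excluding AEs during TI which are more than 70 days after the last dose".
- **Where an interruption begins.** In Section 10.1, "The treatment interruption period starts from 71 days after the last dose". Days 1 to 70 after the last dose therefore belong to the treatment period.
- **The denominator.** Section 10.2 ends exposure 14 days after the final dose. Before a TI it removes only the days of the interruption, so days 15 to 70 stay in exposure there.
- **The effectiveness window.** Section 10.4 writes its rule for one group only: "For patients with TI, effectiveness summaries will combine data from all Treatment Periods". A second clause then sets which values are left out of that pooling, namely "excluding the measurements from 14 days after the last dose during a treatment period up to the first dose in the subsequent Treatment Period".
- **The use.** Section 10.3.3: "To further evaluate the effect of intermittent treatment on the AE profile, rates of AEs per 100 patients-years of exposure to HUMIRA" are analysed by treatment period and by number of TIs. Patients outside the Intermittent Treatment Population are summarised as a reference.

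**The concern.** Worsening of psoriasis is the treated disease returning, that is, an effectiveness outcome seen in reverse. For toxicity with residual drug, a long carry-over is sensible. For this one term, the same carry-over also collects loss of effect after stopping and labels it treatment-emergent.

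This matters most in Section 10.3.3. The Intermittent Treatment Population has at least two TIs per patient, and the reference group has fewer by construction. Each stop opens another stretch in which a flare from loss of effect can enter the numerator. The factor under study, how often treatment is stopped, can then move the AESI rate without any change in the risk of worsening while on drug. The table shell in that section has one rate per cell and does not separate this term or the time since last dose. The tabulation by preferred term in Section 10.3.2 shows the term but cannot tell onset on day 10 from onset on day 45.

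**Working it through.** The protocol states no figure for this point, so there is none to reproduce. The check compares its windows and then does person-time arithmetic on declared assumptions.

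**1. Days treated differently.** 70 − 14 = 56 days before each TI, or 56/70 = 80% of the carry-over. A patient with two TIs has at least 2 × 56 = 112 such days. On these days a PGA or DLQI value is excluded from effectiveness, while a flare counts as a treatment-emergent AESI.

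**2. Effect on the rate before a TI.** Let T be years of dosing, λ the on-drug rate of worsening (per PY), and f the number of worsening events per stop with onset on days 15 to 70. With the protocol's windows:

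rate per 100 PY = 100 × [λ(T + 14/365.25) + f] / (T + 70/365.25)

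T, λ and f are assumptions. With λ = 0.01, so that the rate up to day 14 is 1.0 per 100 PY in every row:

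| T (years) | f = 0.05 | f = 0.10 | f = 0.20 |
|---|---|---|---|
| 1 | 5.1 | 9.3 | 17.7 |
| 2 | 3.2 | 5.5 | 10.1 |
| 5 | 1.9 | 2.9 | 4.8 |

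Example: T = 2, f = 0.10 gives 100 × (0.0204 + 0.10)/2.192 = 5.5. Within a column, only the spacing of stops changes.

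**3. How far a fold-difference depends on assumptions.** Compare cycles of six months' dosing plus 70 days (0.5 + 0.192 = 0.692 PY) with one stop after three years (3 + 0.192 = 3.192 PY), with f = 0.20 and no on-drug worsening:

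- 0.20/0.692 = 28.9 and 0.20/3.192 = 6.3 per 100 PY, ratio 4.6.
- If the three-year user's stop is final and exposure ends at day 14 as in Section 10.2, 0.20/3.038 = 6.6, ratio 4.4.
- Adding an on-drug rate of 10 per 100 PY to both: 38.9/16.3 = 2.4. Adding 20: 48.9/26.3 = 1.9.

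The direction is stable. The size is set by the assumed durations and on-drug rate.

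**4. Would shortening only the numerator work?** In the six-month cycle, events would count over 0.5 + 14/365.25 = 0.538 PY while exposure stays at 0.692 PY. 0.538/0.692 = 0.78, so a constant on-drug rate would be understated by about 22% before each TI and not at all after a final stop. Any split needs its own person-time.

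**The case against.** The strongest reply is that nothing here is contradictory. The 70-day safety window is uniform and deliberate, a safety window longer than an effectiveness window is ordinary practice, and the protocol's own definition admits events from drug withdrawal. A flare after stopping is arguably something an analysis of intermittent treatment ought to show. This stands: the window is not an error, and the point is only that one term is pooled in a way that blurs what Section 10.3.3 can conclude.

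A reader might infer that Section 10.4 declares the drug effect over at 14 days and so conflicts with Section 10.3.2. The text does not support that. Section 10.4 gives no reason for its cut-off and states it only for patients with a TI; for permanent stops it sets no such limit.

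A reader might also infer that relapses after day 70 are lost. They are not. The observational analyses (Sections 10.3.1 and 10.3.4) count events irrespective of treatment. Item 2 of Section 10.3.3 runs from the first injection to the end of the last treatment period and so spans the interruptions. These analyses do not, however, supply the exposure-based comparison by treatment period.

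It is fair, too, that the reference group carries no test or decision rule, and that each period followed by a TI holds exactly one stop. But periods differ in length, and the flare contribution is f divided by that length, so shorter periods still give higher rates.

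Lastly, splitting a term is detail that an analysis plan may hold. If that plan, not shown here, already does so, the point is met.

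**Conclusion.** The point holds in a limited form. For worsening of psoriasis, the treatment-emergent definition pools on-drug events with flares up to 70 days after stopping, and the exposure-based rates in Section 10.3.3 can therefore rise with the number of stops when on-drug risk does not. Attributing any given flare to stopping is an inference; the protocol offers no way to separate the two.

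The size is unknown, since the protocol gives neither a flare rate nor an on-drug rate of worsening. A reader might take the 4.6-fold contrast as an expected bias. It is not: it needs the assumed durations and zero on-drug events, and falls to 1.9 with an on-drug rate of 20 per 100 PY. The observational analyses are unaffected. This is a cheap improvement to interpretation, and it does not call for changing the main safety definition.

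**What to change.** - Keep the 70-day window as the main treatment-emergent definition for every AESI, including this one.
- For worsening of psoriasis only, also tabulate events by onset relative to the last dose of the treatment period: up to day 14, days 15 to 70, and during a TI. Divide each count by the person-time of the same band. After a final stop, the person-time for days 15 to 70 must be computed separately, because Section 10.2 ends exposure at day 14.
- In Section 10.3.3 and its reference summary, show AESI rates with and without this term.

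In the zero on-drug example above, the first band would then be 0 in both groups and the second 0.20/(56/365.25) = 130 per 100 PY in both, so the artificial contrast disappears.

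Cost: a sentence each in Sections 10.3.2 and 10.3.3, a few extra table rows and a footnote. Onset and dosing dates are already collected, and patient management is not touched.

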6.1.1 Inclusion Criteria

A patient will be eligible for participation in this registry if he/she meets all of the following criteria:

1. An adult patient (18 years of age or older) with chronic plaque psoriasis who has been prescribed HUMIRA® therapy according to the local product labeling and meets one of the following criteria:

Newly initiated (within 4 weeks of registry entry) on HUMIRA® therapy; Initiated HUMIRA® therapy in the past and:

Has received continuous (no more than 70 consecutive days off drug) HUMIRA® therapy and the physician can provide source documentation of SAEs, AEs of Special Interest, and dosing information since initiation of therapy.

OR

Is entering after participation in an AbbVie HUMIRA (adalimumab) sponsored study and has received continuous (no more than 70 consecutive days off drug) HUMIRA® therapy after the completion of AbbVie sponsored study and the physician can provide source documentation of SAEs, AEs of Special Interest, and dosing information since initiation of commercial HUMIRA® (defined as a prescribed/non study drug).

- 2. Patient is willing to consent to data being collected and provided to AbbVie.
- 3. Patient is capable of and willing to give written informed consent and to comply with the requirements of the registry.

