10.2 Demographics and Registry Enrollment Characteristics

Demographics and baseline characteristics will be summarized for the All Treated Patient Population, the New Prescription Patient Population, and the Intermittent Treatment Population. Descriptive statistics will be presented. Number of patients with non-missing values, mean, and standard deviation will be provided for continuous variables. Counts and percentages will be provided for categorical variables. The number and percentage of patients that discontinue from the registry will be summarized, overall and by reason for discontinuation. Duration of observation in the registry and total duration of treatment will be summarized as follows:

Duration of observation in the registry is defined from the first day in the registry (enrollment visit or date of informed consent, up to the end-of-registry (as defined in Section 12.0).

The duration of treatment in the registry (registry exposure) is defined from the first dose of HUMIRA® in the registry to 14 days after the last dose of HUMIRA® excluding total days of any treatment interruptions.

Total duration of treatment (total exposure) is defined from the first recorded dose of HUMIRA® (initial dose) to 14 days after the last dose of HUMIRA® excluding total days of any treatment interruptions.

Time to observational and treatment discontinuation will also be presented as Kaplan-Meier (KM) curves.

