10.3.5 Subgroup Analysis of Adverse Events

A summary of SAEs, AEs of Special Interest and AEs that lead to permanent discontinuation of HUMIRA® will be provided by the following:

- 1. By geographic locations.
- 2. By types of physician practices.

For patients exposed to concomitant medications of interest. The categories of
concomitant medications of interest that will be captured include phototherapy,
systemic biologics, systemic non-biologics and PUVA.

[figure not shown]
In addition, the analysis of Observational AEs and the analyses of All Treatment-emergent AE will be performed for the New Prescription Patient Population.

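### Pooled since-first-dose rates in 10.3.2 understate deaths and AEs leading to permanent discontinuation, because prior users had to be alive and still on drug to enrol

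*Protocol*

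**What the plan says.** Five provisions of the Protocol combine.

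- **Entry (6.1.1).** A prior commercial user qualifies if the patient "Has received continuous (no more than 70 consecutive days off drug) HUMIRA® therapy and the physician can provide source documentation of SAEs". The documentation must also cover special-interest events and dosing. A rollover from a sponsor study qualifies if the patient "has received continuous (no more than 70 consecutive days off drug) HUMIRA® therapy after the completion of AbbVie sponsored study".
- **Analysis set (10.1).** "All Treated Patient Population is defined as patients who receive at least one dose of HUMIRA® in the registry".
- **Numerator (10.3.2).** "All Treatment-emergent AEs include AEs occurring from the first recorded dose of HUMIRA® (i.e., the initial dose) up to 70 days after" dosing ends, excluding treatment interruptions. For patients who started earlier, "the summaries will include the events reported during their participation in the previous study, any events reported by retrospective data collection" are added to the registry events.
- **Denominator (10.2).** "Total duration of treatment (total exposure) is defined from the first recorded dose of" the drug, and it ends 14 days after the last dose, less interruptions. Section 10.3.2 refers to Section 10.2 for exposure, and the amendment rationale in Section 1.1 pairs total exposure with the All Treatment-Emergent AEs.
- **Outcomes.** The rates in 10.3.2 cover SAEs, AEs of Special Interest and AEs leading to permanent discontinuation. Under 7.1.3, SAEs include events that result in death.

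Section 10.3 lists this as one of five main safety analyses and does not rank them. Section 10.3.5 adds that "the analyses of All Treatment-emergent AE will be performed for the New Prescription Patient Population".

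**The concern.** A patient who died, or who stopped the drug for good because of an AE, before the registry reached them could not enrol. Everyone in the All Treated Population who started earlier has by selection come through the pre-registry period alive and still on treatment. Counting that period as time at risk for death or for treatment-ending AEs is immortal time: the patient-years go into the denominator while the events are kept out of the numerator.

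Amendment 3 aligned the event window with the exposure window. That does not help, because the problem is who is observed in the window and not where it starts. Section 10.3.2 states no delayed entry at enrolment.

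At stake are the All Treated, All Treatment-Emergent rates of fatal events and of AEs leading to permanent discontinuation. Both would look lower than they are, in a registry whose primary objective is long-term safety.

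**Working it through.** **Inputs from the Protocol**
- Planned observation (10.6): 6,000 patients × 10 years × (1 − 0.40) = 36,000 PY, and 5,000 × 10 × 0.60 = 30,000 PY. Both stated totals reproduce.
- Trial rollovers (6.2): 5% to 10% of patients.
- New Prescription patients (10.1): started within 4 weeks before entry.
- Event window 70 days after last dose (10.3.2); exposure window 14 days after last dose (10.2).

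**Assumptions, because the Protocol gives no figure**
- Share of prior users beyond the rollovers, mean pre-registry years per prior user, and on-drug time as a fraction of observation.

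**Formula.** Let R be registry PY, P pre-registry PY and E the events. If events cannot occur in P, the registry rate is E/R and the pooled rate is E/(R + P). The ratio is R/(R + P), so the dilution is P/(R + P).

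| Prior users (of 6,000) | Mean years before entry | P | R | Dilution P/(R + P) |
|---|---|---|---|---|
| 5% (rollovers) | 1 | 300 | 36,000 | 0.8% |
| 10% (rollovers) | 2 | 1,200 | 36,000 | 3.2% |
| 10% (rollovers) | 4 | 2,400 | 36,000 | 6.2% |
| 50% (assumed) | 1 | 3,000 | 36,000 | 7.7% |
| 50% (assumed) | 2 | 6,000 | 36,000 | 14.3% |
| 50% (assumed) | 3 | 9,000 | 36,000 | 20.0% |
| 50% (assumed) | 1 | 3,000 | 18,000 | 14.3% |
| 50% (assumed) | 2 | 6,000 | 18,000 | 25.0% |
| 50% (assumed) | 3 | 9,000 | 18,000 | 33.3% |

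The last three rows take on-drug exposure as half of observation.

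**Other event types.** Suppose a fraction q of events of a given type is fatal or ends treatment, and the underlying rate is constant. Pre-registry time then shows only (1 − q) of the true rate, and the dilution is q × P/(R + P). It is full for q = 1 and absent for q = 0. Serious events that often end treatment lie in between; events after which treatment continues are little affected. The Protocol gives no q.

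**New Prescription Population.** At most 6,000 × 28/365.25 = 460 PY precede entry. 460/(36,000 + 460) = 1.3%, an upper limit reached only if all 6,000 were new.

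**Opposing mismatch.** Events count for 70 − 14 = 56 days beyond the end of exposure. 6,000 × 56/365.25 = 920 PY, and 920/36,000 = 2.6% at most, in the upward direction. The same gap sits in registry and total exposure, so it does not alter the ratio R/(R + P).

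**The case against.** The strongest reply is that the plan already produces better rates. The Observational analyses and the Registry Treatment-Emergent analysis begin at enrolment or at the first registry dose. The SIRs sit in the Observational analysis, and the lymphoma calculation in 10.6 rests on observation time. Section 10.3.5 repeats the All Treatment-Emergent analysis in patients with at most 4 weeks of prior use. All of this is correct and limits the harm. It does not correct the pooled All Treated rate, and nothing in Section 10.3 warns against reading that rate for deaths or discontinuations.

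Several stronger readings are tempting, and the Protocol does not support them:

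- *Pre-registry time is event-free.* It is not. SAEs and AEs of Special Interest since the first commercial dose are collected (6.5, 6.5.3, 7.4) and counted. Only fatal and treatment-ending events are kept out by selection, and even there an AE with onset before entry may lead to death or stopping afterwards.
- *Retrospective events rest on recall.* Patients are asked, but physician source documentation is an entry condition for prior commercial users. Under-capture is not shown.
- *The rates could be halved.* Against 36,000 PY that needs 36,000 pre-registry PY, or 6 years for each of 6,000 patients, newly started ones included.
- *The conclusion on the primary objective is invalid.* The pooled rate is one of five unranked analyses, and no text makes it the basis for that conclusion.

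It is also fair to say that the 70-day against 14-day mismatch makes the net error in absolute rates smaller than the dilution figures. With rollovers alone the two could be of similar size.

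**Conclusion.** The concern holds for two outcomes in one analysis: deaths, and AEs leading to permanent discontinuation, in the All Treatment-Emergent rates of the All Treated Population. The direction is downward whenever pre-registry exposure exists. Serious events that often end treatment are understated in part.

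The size cannot be fixed from the Protocol. It is about 1% to 6% if the stated rollover share is the only source and each rollover brings an assumed 1 to 4 years. It is about 8% to 20% under an assumed 50% prior users with 1 to 3 years, and 14% to 33% if on-drug time is also only half of observation. These percentages compare the pooled rate with the registry-only rate and are not net of the up to 2.6% upward mismatch.

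The bias comes from entry, numerator and denominator rules that the Protocol itself sets, so it is more than a detail left to the statistical analysis plan. It is worth correcting because the correction is cheap.

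**What to change.** In Section 10.3.2, for the All Treated Population:

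1. Report rates of deaths and of AEs leading to permanent discontinuation on registry exposure only, that is, from the Registry Treatment-Emergent analysis, in which time before enrolment does not count. Do not calculate a pooled since-first-dose rate for these outcomes.
2. Tabulate pre-registry events in a separate table with their own person-years, and note that prior users were selected for being alive and on continuous drug.
3. Take since-first-dose rates for these outcomes from the New Prescription Population, which 10.3.5 already plans.

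No new data are needed: dose dates and event dates are already collected. The cost is fewer patient-years for these two outcomes, hence somewhat wider intervals, and some splitting and relabelling of tables.
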